A retrospective study⁸ was recently conducted in consecutive patients treated for cerebral vasospasm at The University of Texas Medical School, Memorial Hermann Hospital at the Texas Medical Center, a tertiary treatment center in Houston. Two cohorts were involved. Group 1 (N=47 patients, 116 vessels) was treated between 2008-2011 with a single agent; Group 2 (N=69 patients, 106 vessels) was treated between 2010-2013 with a cocktail of multiple agents (nitroglycerin, verapamil, nicardipine). Patient demographics, age, and modified Rankin score (mRS) at discharge and at 3 months were collected in the cerebrovascular database. Arterial luminal diameters were measured in cerebral angiograms both pre-infusion (PrID) and post-infusion (PoID). The Improvement Ratio (IR) = (PoID - PrID/PrID) x 100 was calculated and statistically compared among groups. This study results showed, Group 2 demonstrated a significantly greater improvement IR 45.8% (SD 36.6) than Group 1 IR 10.9% (SD 12.0), P<0.001. Multiple agent therapy. Comparison of the IR between different single agents within Group 1 (nicardipine and verapamil) demonstrated no difference in vessel diameter change. Patient age had no effect on efficacy in either group.

The conclusion of this study is that treatment of cerebral vasospasm with an IA cocktail of nitroglycerine, verapamil, and nicardipine provides significantly better angiographic improvement of vasospasm than does single agent therapy. (This study has been presented at the International Stroke Conference 2014, in San Diego, CA).

This encouraging result has led us to pursue this proposed prospective evaluation of the efficacy of cocktail drug agent infusion therapy versus the current standard of care single agent therapy that is used by the majority of neuro-interventionists throughout the United States.

The goal of this study is to determine the optimal intra-arterial drug treatment regimen for treating cerebral vasospasm.

Given that each of currently commonly used intra-arterial vasodilators (verapamil, nitroglycerin and nicardipine) has its own mechanisms of action despite some of them belonging to the same drug category ⁹, combining these medications for intra-arterial infusion potentially provides synergistic effects of cerebral vasodilation while minimizing cardiovascular instability induced by high doses of single agent treatment.

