Verapamil 10 mg in 10 mL saline, Infusion rate: 1 mL/minute over a period of 10 minutes + Nitroglycerin (200 mcg in 4 mL 5% dextrose, Infusion rate: 0.5 mL/min over 8 minutes + Nicardipine 5 mg in 25 mL 5% Dextrose, Infusion rate 1.25 mL/min over 20 minutes per circulation (USE DIFFERENT SYRINGES FOR EACH DRUG. DO NOT MIX DRUGS IN THE SAME SYRINGE.)

Perform post-treatment angiogram run minimally 10 minutes after completion of infusion. Angiographic Imaging should be recorded 10 minutes after infusion.

ONLY ONE TREATMENT SESSION is permitted per day.

Drug Dosage: Maximum intra-arterial dose allowed within 24-hour period is, nicardipine 10 mg, verapamil 20 mg, cocktail (verapamil 20 mg, nitroglycerin 400 mcg & nicardipine 10 mg)

Please refer to Appendix V & VI for detailed drug dosage tabulations.

If the study subject needs another treatment after the first treatment session, use the same drug for each repeat treatment.

Additional doses can be given per the treating physician's discretion up to the maximum allowed dose as per the protocol; please record the additional doses and treatment given in the data collection forms.

Balloon angioplasty can be performed if drug infusions show insufficient improvement per the treating physician's discretion.

A central core laboratory will perform radiographic data assessment and assessors will be blinded to treatment group assignment.

The diameters of the same spasm vessel(s) will be compared before (pre-) and after (post-) infusion of the agent/agents, (see figure below).

The diameters will be measured at the following locations: ICA supraclinoid segment, MCA M1, MCA M2, ACA A1, ACA A2 & Basilar

The pre-treatment diameter measurement will be at the narrowest spot as is shown in the figure below. The post-treatment diameter measurement will be at the same location as the one prior to the infusion treatment.

Pre-infusion

Post-infusion

The changes will be quantitated based on the ratio percentage as shown in the following formula.

Post-infusion improvement ratio (PIIR) = (B - A)/A

Example: A = 1 mmB = 1.2 mm

PIIR % = (1.2 - 1)/1 = 20%

If balloon angioplasty is performed, the artery diameter will still be measured and the measurement documented.

Clinical data, that will be collected and entered in REDCap are as follows:

- Patient demographics (age, gender, BMI, race)
- Patient medical and surgical history
- Patient's current medications

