- The length of time from aneurysm rupture to time of surgical intervention
- Time in between vasodilator applications
- Number of drug applications used
- Dose of drug applications
- Pre- and post-procedure intracranial pressure measurements (ICPs)
- Cardiovascular instability (SBP changes in mm Hg, requirement of intravenous [IV] pressors)
- New strokes on CT
- Modified Rankin Scale, NIHSS (before treatment, at discharge, and at 3 months after discharge)

Patients will have a 3-month follow-up clinic visit as per standard of care after discharge from the hospital.

5. SELECTION AND ENROLLMENT OF SUBJECTS

Inclusion Criteria: Only adult patients ≥ 18 years with ruptured aneurysms requiring surgery or endovascular therapy and who experience vasospasm post-operatively (3-21 days post-procedure) will be enrolled in this study.

Informed consent will be obtained either from the patient or the patient's legal representative. The institutional PI/Co-PI will determine the **eligibility of the patients** for the study on the basis of the following:

- Adult patient, age 18 80 years old, with ruptured aneurysm(s) who experience vasospasm postoperatively within 3-21 days.
- Symptomatic vasospasm (clinical or TCD)
- For centers that perform a routine day 7 angiogram post-aneurysm treatment 50% or more stenosis seen on diagnostic angiogram for asymptomatic patients.

Exclusion Criteria:

- Inability to obtain consent from patient or patient's family
- Pregnant women (confirmed by a positive pregnancy test)
- Hunt Hess (HH) grade 5
- Intra-arterial drug treatment in all 3 arterial territories

Study Centers:

The University of Texas Medical School at Houston University of Illinois College of Medicine – Chicago Geisinger Health System, North Shore University Hospital – Northwell Health

Study Enrollment Procedures:

Institutional PI & Co-PI will determine a patient's eligibility based on SOC testing and procedures used in treating patients with aneurysms.

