10. STATISTICAL CONSIDERATIONS

Design:

The clinical trial will be conducted under a common umbrella protocol developed by the primary site (UTH) with the intention of combining data from all satellite centers for analysis. Each investigational site will give utmost importance to follow the study protocol to maintain consistency in study execution at all centers. Patients will be randomly assigned to 3 treatment groups in a 1:1:1 allocation ratio. The three therapeutic regimens to be considered are:

Group 1: nicardipine (Cardene) 5 mg per circulation in 25 mL of 5% Dextrose,

Group 2: verapamil 10 mg per circulation in 10 mL saline

Group 3: Cocktail agents: 5 mg in 25 mL 5% Dextrose + verapamil 10 mg in 10 mL saline + nitroglycerin 200 mcg in 4 cc of D5W per circulation.

A maximum of 330 subjects, 110 per treatment arm, will be randomized. The trial includes interim analyses that may reduce the maximal sample size if clear differences emerge among the arms during the conduct of the trial.

Interim Analyses:

Interim analyses will be performed to allow for discontinuing enrollment to treatment arms due to futility. After approximately 90 subjects have been randomized, 30 per arm, interim analyses will begin at the next quarterly Data and Safety Monitoring Board (DSMB) meeting. Subsequent interim analyses will be performed to coincide with DSMB meetings, which will occur after 40 subjects, 70 subjects, 110 subjects, 165 subjects, and 248 subjects have completed the study, and at the conclusion of the study (330 subjects).

At each interim analysis, an Analysis of Variance (ANOVA) will be performed to compare the PIIR results across treatment arms. If the overall treatment effect is significant with a p-value<0.05, then pairwise treatment comparisons will be performed. If any pairwise comparison is significant at a Tukey's adjusted two-sided p-value of 0.02 (p< 0.02), the poor performing arm will be dropped from the randomization scheme. If multiple arms are dropped and only one treatment arm remains open for randomization, that arm will be declared as best, and the clinical trial will end. Pairwise comparisons will only be performed if the overall treatment effect in the ANOVA is significant.

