Additional secondary outcomes include SAE (severe adverse event) occurrences and the rate of treatment failure with balloon angioplasty. These outcomes will be summarized descriptively by presenting rates and proportions. Exploratory analyses comparing outcomes between treatment arms will be made using a Chi-square test.

Additional exploratory multivariable linear regression models will be created for the PIIR outcome, adjusting for treatment groups and additional baseline factors.

The analyses for the secondary outcomes are considered exploratory and no adjustments for the multiple tests and multiple comparisons will be made. Results will be interpreted cautiously understanding the some results may be significant at the 5% level due to chance alone.

Sample Size Justification:

Simulations were performed to estimate the power of the study for the primary outcome measure, PIIR, with a maximum sample size of 330 (110 per treatment arm) and the interim analyses for possible early arm dropping. A range of scenarios of PIIR were examined; the key scenarios used to power the trial are presented in Table 2.

Table 2.

Scenario	Treatment Arm 1: Nicardipine (N)	Treatment Arm 2: Verapamil (V)	Treatment Arm 3: Combination (C)
Combo 20	0.10	0.10	0.30
Mixed 1530	0.10	0.15	0.30

Note that the scenarios are both in favor of Verapamil over Nicardipine, but the results are symmetric if Nicardipine and Verapamil were reversed.

The trial will make every pairwise comparison:

- N versus V
- N versus C
- V versus C

The simulations focused on the V>N, C>N, and C>V comparisons. The following table presents the expected (mean) sample size and probability that the combination treatment regimen is better than the verapamil regimen, i.e., Pr(C>V), the main comparison of interest. Power is defined as the probability of identifying the superiority of the best dose over the other two doses.

Table 3.

Scenario	Expected N	Power Pr(C>V)
Combo 20	177	0.95
Mixed 1530	211	0.77

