APPENDIX

- I. List of Participating Centers:
- 1. The University of Texas Medical School at Houston
- 2. University of Illinois in Chicago
- 3. Geisinger Health System
- 4. North Shore University Hospital Northwell Health
- 5. Memorial Hermann Hospital- At The Woodlands

II. Drug Information: The dose of the each medication set in this study is based on the limited clinical data available for each agent.

1) Nicardipine: a dihydrophyridine calcium channel blocker, the therapeutic effect is believed to be related to the selective inhibition of transmembrane calcium ion influx into vascular smooth muscle, resulting in a reduction of free calcium ions in these cells and disruption of actin-myosin interaction essential to muscle contraction ⁹. The dose used frequently in IA therapy is ranges 2 - 25 mg/each arterial territory, mean dose 5.7 +/- 4.3 mg ⁶. High dose IA nicardipine results hypotension, in some cases, even dose ranging from 4 to 7.5mg.

2) Verapamil: a phenylalkylamin calcium channel blocker that inhibits voltage-gated calcium channels in the arterial wall smooth muscle cells and results in vasodilation. It has been observed that there were no significant changes in BP, HR or ICP after administration of more than 20mg of IA verapamil ⁵.

3) Nitroglycerin: has been used in cerebral vasospasm treatment for a couple of decades. It has been reported dose of single vascular territory used up to 700 mcg without major hemodynamic instability.

III. Adverse events:

Term	Definition
Adverse Event (AE)	Any untoward medical occurrence, unintended disease or injury, or untoward clinical signs (including abnormal laboratory findings) in subjects, users or other persons, whether or not related to the investigational drugs.
	NOTE 1 This definition includes events related to the investigational drugs. NOTE 2 This definition includes events related to the procedures involved.
Adverse drug effect	Any AE related to the use of an investigational drug.

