Serious adverse event	 Any AE that a) led to death, b) led to serious deterioration in the health of the subject that either resulted in 1) a life-threatening illness or injury, or 2) a permanent impairment of a body structure or a body function, or 3) in-patient or prolonged hospitalization, or 4) medical or surgical intervention to prevent life-threatening illness or injury or permanent impairment to a body structure or a body function, NOTE: Planned hospitalization for a pre-existing condition, or a procedure required by this Protocol, without serious deterioration in health, is not considered a serious adverse event. (ISO 14155, 2011)
Technical Event	A study procedure related event.
Stroke	New Stroke event, worsening of motor, sensory or speech function. Cant be explained by cerebral vasospasm and or pre-existing aSAH Clinically and radiographically.
Neurologic Death	For the purposes of study endpoints, neurologic death is defined as any death determined to be of neurologic cause. This definition excludes: death due to rupture of a nonindex aneurysm or as a consequence of treatment of a nonindex aneurysm.
Death	For the purposes of study endpoints, death excludes death of accidental causes or death due to rupture of a nonindex aneurysm or as a consequence of treatment of a nonindex aneurysm.

Study procedure related Minor complications might include:

Nausea and/or vomiting (post-anesthesia) Mild headache Groin discomfort: mild pain and or bruising at the incision site

Study Procedure related **Significant complications** (catheter induced: different from preexisting cerebral vasospasm & SAH induced ischemia): Intra-cranial catheter induced spasm of the treated segment of artery or branches Stroke (ischemic, hemorrhagic, TIA) Hemiplegia Aphasia Visual impairment or blindness Intra cranial artery tear (hemorrhage) Femoral artery occlusion due to catheter

Study Procedure related Very Rare side effects may include: Death Renal failure due to dye induced Seizure Infection Blood vessel or nerve damage Decreased blood flow in the leg on the side of the groin puncture A pseudoaneurysm may develop as a result of injury to all the layers of a vessel wall resulting in a hematoma Air embolism Mental status changes Total occlusion of the treated blood vessel segment or other blood vessels.

DRUG RELATED adverse events & overdose effects:

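### Systolic pressure change and IV pressor need are collected, but hypotension short of a serious adverse event has no planned comparison between the cocktail and the same-dose single agents

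*Combined protocol and SAP*

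**What the plan says.** **Collection.** Section 4 introduces a list with "Clinical data, that will be collected and entered in REDCap are as follows", and one item on it is "Cardiovascular instability (SBP changes in mm Hg, requirement of intravenous [IV] pressors". No timing or metric is attached to the SBP item. The Monitoring Plan in Appendix III adds blood pressure, heart rate, ECG, arterial pressure and intracranial pressure during the procedure, and data every 12 hours before and after it.

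**Analysis.** Section 10 (Final Analyses) compares PIIR by ANOVA and 3-month mRS by chi-square. On safety it then says: "Additional secondary outcomes include SAE (severe adverse event) occurrences and the rate of treatment failure with balloon angioplasty". These are summarised as rates and proportions, with exploratory chi-square tests between arms. Section 10 names no summary of SBP change, pressor need, hypotension or non-serious events.

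**Dose.** The 24-hour maxima in Section 4 are "nicardipine 10 mg, verapamil 20 mg, cocktail (verapamil 20 mg, nitroglycerin 400 mcg & nicardipine 10 mg".

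**Serious-event line.** For an event short of death, life-threatening illness, permanent impairment or hospitalisation, the Appendix III clause that could apply is "medical or surgical intervention to prevent life-threatening illness or injury or permanent impairment to a body structure or a body function".

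**Decision rule.** Interim arm-dropping uses PIIR. If one arm is left, "that arm will be declared as best, and the clinical trial will end".

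**The concern.** Hypotension is a foreseeable drug-specific harm of intra-arterial vasodilators. Appendix II says of nicardipine: "High dose IA nicardipine results hypotension, in some cases, even dose ranging from 4 to 7.5mg". That range includes the 5 mg infusion used in Groups 1 and 3. The cocktail adds verapamil and nitroglycerin to it without lowering either calcium-channel-blocker dose relative to the single-agent arms.

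If the plan is followed as written, the cocktail can be declared best on vessel diameter with no planned estimate of how much more (or less) sub-serious hypotension or pressor support it brings than either single agent. The relevant data would be in hand, but any table built from them would be chosen after the results were known.

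**Working it through.** The plan states no figure on this point, so there is nothing to reproduce. The check is a match of what is collected against what is analysed, followed by illustrative arithmetic.

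**1. Dose stacking (Section 4).** Cocktail against single-agent 24-hour maxima: nicardipine 10/10 mg = 100%; verapamil 20/20 mg = 100%; nitroglycerin 400 mcg on top.

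**2. Collected against analysed.**

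| Item | Collected | By-arm comparison in Section 10 |
|---|---|---|
| PIIR, mRS | yes | yes |
| SAEs, treatment failure with balloon angioplasty | yes | yes, exploratory |
| SBP change, IV pressor need | yes (Section 4) | none named |
| Intra-procedure blood pressure | yes (Appendix III) | none named |

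The DSMB text does not fill the gap. The items listed just before the quarterly summaries in Section 11 are not haemodynamic, and the adjudication list at the end of Appendix III does not name hypotension.

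**3. What the SAE comparison would see.** The documents give no pressor rate and no share of episodes that would be classed as serious, so both are assumed. With true pressor need of 20% against 40%, and a share f of episodes in each arm classed as SAEs, the visible difference is f × (40 − 20) points. At 110 per arm:

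- f = 0.25: 5 points, 95% CI −1.9 to 11.9
- f = 0.50: 10 points, 0.7 to 19.3
- f = 0.75: 15 points, 4.1 to 25.9

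**4. Precision of a direct comparison.** SE = √[p₁(1−p₁)/n₁ + p₂(1−p₂)/n₂]; CI = difference ± 1.96 × SE. Arm sizes: the 110 maximum; 70 against 110 from the dropped-arm example in Section 10; and the expected N of 177 under Combo 20, split equally (177/3 = 59) or unequally (50 + 50 + 77 = 177).

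| n per arm | 20% vs 40% | 10% vs 20% |
|---|---|---|
| 110 / 110 | SE 0.0603; 8.2 to 31.8 | SE 0.0477; 0.7 to 19.3 |
| 70 / 110 | SE 0.0668; 6.9 to 33.1 | SE 0.0523; −0.3 to 20.3 |
| 59 / 59 | SE 0.0823; 3.9 to 36.1 | SE 0.0651; −2.8 to 22.8 |
| 50 / 77 | SE 0.0795; 4.4 to 35.6 | SE 0.0623; −2.2 to 22.2 |

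For mean SBP change, half-width = 1.96 × SD × √(1/n₁ + 1/n₂). With an assumed SD of 15 to 25 mm Hg it is 4.0 to 6.6 mm Hg at 110/110, 4.5 to 7.5 at 70/110, and 5.4 to 9.0 at 59/59.

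**5. Exposure time (Section 4 rates).** Per infusion: nicardipine 20 min, verapamil 10 min, cocktail 10 + 8 + 20 = 38 min if the drugs are given in sequence (assumed). With the two infusions per session allowed in Section 6: 40, 20 and 76 min. The time at risk within the procedure therefore differs by design.

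**The case against.** The other side has real force.

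- **Serious cases are covered.** Hypotension that meets the Appendix III definition is an SAE and is compared by chi-square. Marked hypotension stops the drug, every infusion is under anaesthetist care, and the DSMB weighs risk against benefit. A reader might infer that haemodynamic safety goes unmonitored; the documents do not support that. Only the by-arm comparison below the serious line is missing.
- **The rationale is not contradicted.** The Background says that combining agents "potentially provides synergistic effects of cerebral vasodilation while minimizing cardiovascular instability induced by high doses of single agent treatment". A reader might infer that the trial leaves its own rationale untested, or that undiminished component doses refute it. That sentence contrasts the cocktail with high single-agent doses. Appendix II gives a nicardipine range of 2 to 25 mg per territory, and no high-dose arm exists here. The comparison proposed below would not test that contrast, and lower instability is not a stated objective or hypothesis.
- **Evidence of excess risk is mixed.** A reader might infer that the cocktail will cause more hypotension. Appendix II also reports no significant change in blood pressure after more than 20 mg of verapamil, and no major instability with nitroglycerin up to 700 mcg in one territory; the cocktail's daily maxima are 20 mg and 400 mcg. The nicardipine dose is the same in Group 1. Additive hypotension is not ruled out, but it is not shown.
- **The list may not be closed.** The wording of the secondary outcomes does not bar a further descriptive table. True, but none is named.

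What survives is narrow: a foreseeable drug effect, recorded by every site, without a planned by-arm estimate below the SAE threshold.

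**Conclusion.** The point holds as a minor gap in the safety analysis. Hypotension and pressor use short of the serious-event definition have no planned comparison between the cocktail and the same-dose single agents. The primary conclusion, sample size, power and type I error control are untouched.

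The size of the gap cannot be derived from the documents. Under the assumed 20% against 40%, the SAE table would show 5 to 15 of the 20 points as the serious share runs from 25% to 75%. A direct comparison would be informative for a difference that large and imprecise for 10% against 20%, especially after early arm-dropping. The rates, SDs and shares are illustrations; the finding rests on the text, not on them. It also takes SAE in Section 10, spelled out there as severe, to mean the serious event defined in Appendix III.

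**What to change.** In Section 10, after the existing secondary outcomes, add two descriptive safety outcomes for the first treatment session, so that each patient counts once. Analyse them by randomised arm, with differences and 95% CIs:

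- **SBP change:** lowest intra-procedure SBP minus last pre-infusion SBP, from the pressures already recorded under the Monitoring Plan. Section 4 leaves the metric open, so it should be fixed before any by-arm look. The 12-hourly records are supplementary at most, since they can miss a transient fall.
- **New or increased IV pressor requirement:** relative to pre-procedure status. Report patients whose earlier status is unknown separately rather than counting them as events.

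Give the DSMB both by arm beside PIIR at each look.

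The cost is a few tables, with no new patients, procedures or alpha. They are unpowered and need care in reading. Treating physicians know the arm and decide on pressors, so pressor use should be read beside measured SBP. All patients are under general anaesthesia. Infusion time differs by regimen and is part of what is being compared.

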Table 3 demonstrates, that for a hypothesized scenario of "Combo 20" where the combination therapy PIIR is 0.30 compared to 0.10 in Nicardipine and Verapamil, the study will have over 90% power and an expected sample size of 177. Both the Nicardipine and Verapamil arms would have been dropped at interim analyses before they reached their maximum enrollment of 110. If the scenario of "Mixed 1530" is observed, a situation where the Nicardipine arm PIIR is 0.10, the Verapamil arm PIIR is 0.15 and the combination arm is 0.30, the study will have 77% power and an expected sample size of 211. Again, both the Nicardipine and Verapamil arms would have been dropped at interim analyses before they reached their maximum enrollment of 110.

Missing Data and Dropout Rate: We do not anticipate missing data for the primary outcome PIIR as the angiogram will be performed 10 minutes post-infusion. For the secondary outcome, mRS at 3-months, based on previous studies, we estimate up to a 20% loss follow-up. Efforts will be made to keep all patients in the study through the 3-month follow-up visit. Substantial efforts will be made to ensure complete follow-up. Rates of missing data and loss to follow-up will be reported by treatment arm. We will attempt to document maximum amount of information regarding the status of these

patients who drop out. This procedure will help to compare characteristics of those patients who completed the study with those who did not.

Data and Safety Monitoring:

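### Table 3 does not say whether 0.95 and 0.77 are the power as defined (best regimen beats both others) or Pr(C>V) alone, and the early dropping of both single-agent arms is stated as certain when the plan's own figures show it is not

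*Combined protocol and SAP*

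**What the plan says.** All of this is in the combined protocol and SAP, Section 10, Sample Size Justification.

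- The table is introduced as giving the expected sample size and the "probability that the combination treatment regimen is better than the verapamil regimen, i.e., Pr(C>V), the main comparison of interest".
- The next sentence gives a different definition: "Power is defined as the probability of identifying the superiority of the best dose over the other two doses".
- The column in Table 3 is headed as power and as Pr(C>V) together. It shows 0.95 with expected N 177 (Combo 20) and 0.77 with expected N 211 (Mixed 1530).
- The text after the table uses these values as the power of the trial: "the study will have over 90% power and an expected sample size of 177" for Combo 20 and "the study will have 77% power and an expected sample size of 211" for Mixed 1530.
- For each scenario it then says what happens to the single-agent arms. The Mixed 1530 sentence is "Again, both the Nicardipine and Verapamil arms would have been dropped at interim analyses before they reached their maximum enrollment of 110"; the Combo 20 sentence is the same apart from its first word. Neither gives a probability.

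Pr(C>N), the joint probability, the probability of dropping each arm and the SD used in the simulations are not reported.

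**The concern.** Beating verapamil is one event; beating verapamil and nicardipine in the same trial is a smaller one. The two probabilities differ unless every win over verapamil comes with a win over nicardipine. The joint event matches the aim of the trial: Section 2 seeks the optimal regimen and hypothesises that the cocktail improves on single agents, and the interim rules declare an arm best only when it alone remains open. If the column holds Pr(C>V), the power for that aim is somewhat below the printed figures.

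The statements on arm dropping raise a separate issue. Sites, the IRB and the DSMB may read them as a forecast that neither single-agent arm will fill. Under Mixed 1530 the plan's own 0.77 already rules that out as a certainty.

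**Working it through.** **Inputs from the plan.** Mean PIIR for N, V and C is 0.10, 0.10, 0.30 (Combo 20) and 0.10, 0.15, 0.30 (Mixed 1530). The maximum is 110 per arm. At each interim, ANOVA at 0.05 is the gate and the worse arm of a pair is dropped at Tukey-adjusted p<0.02. The final analysis uses ANOVA at 5% and then Tukey-adjusted p<0.0330. Six interim analyses over two years are anticipated.

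**Inputs that must be assumed.** The SD is not given for the simulations. The only SDs in the plan are retrospective (36.6 and 12.0 percentage points, Section 3), and they do not reproduce Table 3. With 0.12, 0.12 and 0.366 by arm, expected N is 115 and 142 with Pr(C>V) 1.00 and 0.97. With a common 0.366, it is 195 and 226 with 0.94 and 0.73. The look schedule is also open, because Section 10 describes both a start at about 90 randomised at quarterly meetings and looks at 40, 70, 110, 165 and 248 completers.

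**Step 1: bounds that need no SD, reading the column as labelled.**

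- Joint power = P(C beats N and C beats V) ≤ Pr(C>V). So it is at most 0.95 and 0.77.
- Also P(A and B) ≥ P(A) + P(B) − 1. In Combo 20, N and V have the same mean, so by symmetry Pr(C>N) = Pr(C>V) = 0.95, and joint power ≥ 0.95 + 0.95 − 1 = 0.90.

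**Step 2: bound on dropping both arms.** V leaves at an interim only after losing a pairwise test. Ignoring the negligible chance that it loses to N, and counting interim wins as wins, P(both dropped) ≤ Pr(C>V).

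- Combo 20: it fails in at least 1 − 0.95 = 5% of trials.
- Mixed 1530: it fails in at least 1 − 0.77 = 23% of trials.

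If the column is really joint power, the same bounds hold, because both arms can be dropped only if C has beaten both (again ignoring single-agent arms losing to each other). Actual failure is more frequent, since some wins come only at the final analysis, after the arms are full.

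**Step 3: simulation of the stated rules.** Normal PIIR with a common SD, Tukey-Kramer tests, all data retained, no outcome lag. Schedule A is 90 then every 41 (330 over 8 quarters is about 41; six interims). Schedule B is 90 then every 30. Schedule C is 40/70/110/165/248. A and B used 25,000 trials per cell.

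| Scenario | Looks, SD | Expected N | Pr(C>V) | Joint | Both dropped at an interim |
|---|---|---|---|---|---|
| Combo 20 (printed 177; 0.95) | A, 0.345 | 181 | 0.966 | 0.940 | 0.871 |
| | B, 0.35 | 177 | 0.964 | 0.937 | 0.879 |
| | C, 0.35 | 188 | 0.963 | 0.932 | 0.780 |
| | C, 0.36 | 196 | 0.952 | 0.916 | 0.751 |
| Mixed 1530 (printed 211; 0.77) | A, 0.345 | 215 | 0.789 | 0.777 | 0.658 |
| | B, 0.35 | 211 | 0.783 | 0.771 | 0.676 |
| | C, 0.35 | 220 | 0.774 | 0.761 | 0.569 |
| | C, 0.36 | 229 | 0.731 | 0.714 | 0.509 |

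Schedules A and B come close to Table 3, to within about 2% on N and 2 points on Pr(C>V). This is a calibration to the table, since the SD was chosen to fit it.

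- Gap between Pr(C>V) and joint power: 0.966 − 0.940 = 2.6 points to 0.952 − 0.916 = 3.6 points in Combo 20; 0.789 − 0.777 = 1.2 points to 0.731 − 0.714 = 1.7 points in Mixed 1530.
- Failure of the dropping statement: 1 − 0.879 = 12% to 1 − 0.751 = 25% in Combo 20, and about 10% at the most favourable setting with SD 0.34 to 0.36. In Mixed 1530 it is about 31 to 45% over most settings, and 1 − 0.509 = 49% in the least favourable row shown.

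**The case against.** The strongest reply is that nothing operative is wrong. No threshold, maximum sample size or analysis depends on this paragraph. Verapamil is the nearer competitor in Mixed 1530, so Pr(C>V) and joint power nearly coincide there. In Combo 20 the bound keeps joint power at 0.90 or above, and simulation gives about 0.91 to 0.95, so the claim of more than 90% power is not shown to be false. The column may already hold joint power under a wrong heading: the simulated joint values lie within about 2 points of the printed ones when the SD is fitted to Table 3. The sentences on dropping can be read as describing a typical trial, and elsewhere Section 10 is conditional, saying that interim analyses may reduce the sample size. All of this stands as a limit on size. It does not settle which quantity the column holds, and an average statement is not what the two sentences say.

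A reader might go further and infer that the printed N and Pr(C>V) cannot both be right, or that expected N is understated. The documents do not support this. The SD is unstated and the schedule is ambiguous, and SD 0.35 with looks every 30 gives N 177 and 211 with Pr(C>V) 0.96 and 0.78, about one point from Table 3. That schedule has more than six looks, but it shows that the mismatch seen under other settings comes from the assumptions.

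A reader might also infer that the planned saving in patients is overstated because arms are not always dropped. That does not follow: expected N is described as a mean, so it already averages over trials in which arms stay open.

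**Conclusion.** Two points hold. First, power is defined as a joint probability and reported as a single comparison, so the meaning of 0.95 and 0.77 is unclear. Read as labelled, they imply power as defined of 0.90 to 0.95 (Combo 20) and at most 0.77 (Mixed 1530), likely 2 to 4 and 1 to 2 points below Pr(C>V). This is a conflict of definition with a modest numerical effect; it does not show that the trial is underpowered. Second, the early dropping of both single-agent arms is presented as certain. It fails in at least about 5% and 23% of trials on the plan's own figures, and in about 10 to 25% and 31 to 45% by simulation. The overstatement matters most for Mixed 1530.

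The bounds count a win at any look. Counting only final-analysis wins moves Pr(C>V) by about a point or less in most runs. The simulated ranges rest on an assumed common SD of 0.34 to 0.36, normal outcomes and assumed look schedules. Two features were not modelled: enrolment continues during interim analyses, and Section 11 counts a subject as complete only after 90-day follow-up and core-lab reading. Both make dropping before 110 less likely.

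**What to change.** In Section 10, Sample Size Justification:

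1. State which probability the Table 3 column holds.
2. Report both Pr(C>V) and Pr(C beats N and V) for each scenario from the existing simulation, with the SD and the look schedule used.
3. Quote the joint value wherever the text refers to the power of the study.
4. Replace the two statements that both single-agent arms are dropped with the simulated probability that both are dropped before reaching 110.

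The cost is one relabelled and extended table and a few reworded sentences. The stated power may become a few points less favourable. Enrolment, interim rules and the final analysis stay as they are.
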